Appendix B: Frequently Asked Questions

The frequently asked questions will be hosted by Mosie Baby on their website. There will be a hyperlink within the survey tool on the consent form allowing participants to be able to access the frequently asked questions at any time.

The following page shows the text of the FAQ.

Appendix C: Participant Recruitment Emails

This section contains samples of the participant recruitment emails.

Note: These are samples. Final language and appearance might be tweaked.

MOSIE-001 © 2020 Mosie Baby Page 84

Initial Email

From: Mosie Baby <[contact]>
Subject: [PREVIEW] Tell us what you really think

Date: July 30, 2020 at 2:18:03 PM CDT To: [name] <[contact]>

mosie baby

Hello [name],

Thank you for using the Mosie Kit on your journey to conceive! To help improve the experience of future Mosie users, we are conducting a clinical research survey. And we would love to hear from you! Your feedback will help others on their journey to conceive through home insemination. Are you open to sharing your anonymous thoughts in our survey?

Participate Now

All information shared will be confidential and private. The survey will take approximately 10-25 minutes to complete. Plus, when you hit submit, you'll receive a **15% discount code** for future purchases. If you have any questions about this survey or anything Mosie Baby, please feel free to reply to this email. Either way, thank you for being a part of the Mosie Community! We appreciate you and are continually rooting for you!

Sincerely, [name] CEO & Co-founder

Second email (approximately 1 week later)

From: Mosie Baby <[contact]>

Subject: [PREVIEW] Help Us Make Mosie Baby Even Better!

Date: July 30, 2020 at 2:21:11 PM CDT **To:** [name] <[contact]>

mosie baby

Hello [name],

Sending you a quick reminder that you've been invited to participate in a clinical research survey about home insemination with the Mosie Kit. In the fertility industry, most research tends to be around IVF and not about home insemination. We hope to help change that!

Please share your insight with us and help improve the home insemination process for others - and also help us show how important home insemination is to the fertility industry!

Everything you share is confidential. Plus, once you hit submit on your survey you'll receive a discount code for 15% off your next order!

To participate in the survey, click below.

Thank you! Sincerely,

[name]

Co-founder of Mosie Baby

Take the Survey

MOSIE-001 © 2020 Mosie Baby Page 86

Third Email (approximately 2 weeks after initial email)

From: Mosie Baby <[contact]>

Subject: [PREVIEW] Two weeks left to share your feedback privately 🌳

Date: July 30, 2020 at 2:39:12 PM CDT **To:** [name] <[contact]>

mosie baby

Hello [name],

Sending you a friendly reminder that our clinical survey closes in two weeks. Please share your feedback and help us improve! Everything you share is confidential. Once you hit submit on your survey you'll receive a discount code for **15% off** your next order!

Participate Now

Thank you to everyone who has participated! It is anonymous so we have no idea if you already have and that's why you keep getting our reminder emails:) If you'd like to stop receiving emails about this survey, click here.

Thank you! Sincerely, [name]

CEO & Co-founder

Fourth email (third week)

From: Mosie Baby <[contact]>

Subject: [PREVIEW] One week off to get your 15% off code!

Date: July 30, 2020 at 2:31:50 PM CDT To: [name] <[contact]>

mosie baby

Hello [name],

Time is running out and this is the final week to participate in our clinical research survey. Your experience is important to us and will make a difference for others doing home insemination. Plus, you'll get 15% off your next order once you submit your survey answers. If you'd like to stop receiving emails about this survey, click here. Sincerely,

[name]

[name]

CEO & Co-founder

Participate Now

Final email reminder (approximately 24 hours prior to study close)

From: Mosie Baby <[contact]> Subject: [PREVIEW] LAST CHANCE for 15% off!
Date: July 30, 2020 at 2:34:45 PM CDT
To: [name] <[contact]>

Hello [name],

Time is running out. This survey ends tomorrow! Your opinion is important to us...

Please share your thoughts and make a difference for others by completing the survey below. Plus, you'll get 15% off your next order once you complete the survey.

Thank you! Sincerely, [name]

CEO & Co-founder

Participate Now

MOSIE-001 © 2020 Mosie Baby Page 88

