The secondary objective(s) are to understand the user's experience with the Mosie Kit and it's safety.	Secondary endpoints are: perceived ease of use and perceived safety.	The perceived ease of use is being examined as a secondary endpoint because being able to follow the instructions and use the kit as designed will directly affect whether the semen is deposited at or near the cervix having a direct effect on the results. Perceived ease of use is viewed as a mediating variable. Finally, perceived safety of the Mosie Kit will be examined. It is expected to be a moderating variable.	In order for the delivery of sperm at or near the cervix, the user needs to maximize the sperm drawn up into the Mosie syringe, insert it into the vagina, and deposit the sperm at or near the cervix. Because the Mosie syringe is inserted into the vagina, it is important to understand any perceived issues or concerns related to safety and use of the syringe.
Tertiary/Exploratory			
The tertiary objective will be to examine the pregnancy rate of people with different self-reported sources of infertility. Given the Pandemic, exploratory effect of COVID-19 on family planning, stress and pregnancy results will be examined.	Because the reason for a person's or couple's infertility might affect pregnancy rates, the reason for the infertility will also be examined. This will provide information as to whether the Mosie Kit is more effective given a specific source of infertility. The pandemic has caused an overall increase in stress, higher stress can affect fertility.	The source of infertility may play a mediating role in a successful pregnancy. For example, it might be more likely that a couple with a woman with no known infertility issue using Mosie might be more likely to get pregnant than a woman with a specific known infertility issue. Stress can play a mediating role in pregnancy. Concern over future stability and	Women who do not have a fertility issue might be more likely to get pregnant when the sperm is successfully deposited at or near the cervix. For example, this would help if the infertility was rooted in Erectile Dysfunction (ED). Stress hormones can affect pregnancy outcome. Stressful and uncertain times make people more

Page 14

planning may be family planning. expanding their families.
--

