Analysis: Descriptive statistics surrounding the ease of use on a 5-point likert (very easy to very difficult) will be analyzed on five different aspects of use. Specifically, the steps of using the Mosie Kit (collecting a sperm sample, drawing up the sample in the Mosie syringe, inserting the syringe, and depositing the sperm at or near the cervix) and overall ease of use will be examined. Additionally questions related to use such as comfort, ease and safety of the process, enjoyable and intuitiveness of use (able to use it without instructions) will allow the user to rate their experience from Strongly agree to strongly disagree (5 point scale). The data will be plotted and examined as part of the analysis.

Secondary Hypothesis 2: The participants were able to use the Mosie Kit as instructed using the instructions contained in the kit. The alternative hypothesis is that the participants were not able to use the kit using the instructions contained in the kit.

Analysis: Descriptive analysis of perceived overall success rate will be analyzed. Additionally, descriptive analysis of the frequency of each expected behavior related to use of the kit will be examined.

Secondary Hypothesis 3: The participants reported they used the kit as intended, specifically, using it within 24 hours of initial signs of ovulation and again 24-48 hours after ovulation was confirmed or expected. The alternative hypothesis is that the participants report they did not use the kit as intended with respect to timing (within 24 hours of initial signs of ovulation and again 24-48 hours post ovulation).

Analysis: Frequency rates related to timing of insemination at all reported cycles will be analyzed. The data will be reported in both total number of attempts at each time point as well as percentage of attempts at each time point in comparison with total cycles where the Mosie Kit was used. T-tests will also be used in this analysis. Additionally,

amount of time lying after insemination and position of lying will be analysed using descriptive statistics and correlations with pregnancy rate.

Secondary Hypothesis 4: Participants reported they perceived the Mosie Kit to be a safe way to conceive. The alternative hypothesis is that participants did not perceive the Mosie Kit to be a safe way to conceive.

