10.1.3 Confidentiality and Privacy

Participation in this study is completely anonymous. Participants will receive an invitation email with a generic link to the study website. Once informed about the study and its participation, the participant can respond to the survey questions without entering any identifiable information. The PI deemed the value of obtaining any identifying information was inferior to protecting the participant's privacy and that it was unnecessary for this study. Therefore, no identifying information will be collected. There will be no identifiers that can link directly back to an individual. While information about race, gender, and age will be collected, it will not be possible to point the information back to any given individual.

Invitations to participate will be sent out by the Sponsor company. The full list of those emails will never be released to the PI. This will help keep the information from being able to be linked back to the group of emails sent.

The final database will be an anonymous database that will be the property of the Sponsor. There is currently no intent to share the results of that study beyond this research. There is an intent to publish the findings of the study as a journal article and for information on the Sponsor's company website, but this information will be limited to aggregate results and to discussions related to the findings. The Sponsor might also use aggregate data or results in future marketing materials.

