10.1.12 Conflict of Interest Policy

The independence of this study from any actual or perceived influence, is critical. In order to ensure the integrity of this research, any conflict of interest of persons who have a role in the design, conduct, analysis, publication or any aspect related to the trial will be disclosed and managed. The PI reports that this study is a work for hire by the Sponsor. There is no other known conflict of interest.

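### The second recruitment email asks recipients to help make a case for home insemination, which could tilt who answers and how they rate the kit; neutral wording is a cheap improvement

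*Combined protocol and SAP*

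**What the plan says.** Section 5.5 schedules five emails, the second on Day 7. Section 10.1.3 states: "Invitations to participate will be sent out by the Sponsor company". The sample text of the second email in Appendix C remarks that fertility research mostly concerns IVF, expresses the hope of changing this, and asks the recipient to share insight, to help improve the process for others and to "also help us show how important home insemination is to the fertility industry". The signature reads "Co-founder of Mosie Baby". The appendix adds: "Note: These are samples. Final language and appearance might be tweaked".

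Section 3 states: "Secondary endpoints are: perceived ease of use and perceived safety". In section 9.1, Secondary Hypothesis 1 is examined with five-point ratings of ease. Secondary Hypothesis 4 is worded "Participants reported they perceived the Mosie Kit to be a safe way to conceive" and is examined descriptively. Secondary Hypothesis 5 asks whether a majority have little or no safety concern. None of these analyses has a comparator.

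Section 6.3, on bias, relies on inviting all purchasers in the window. It does not address who chooses to answer or how the invitation is framed. Section 10.1.12 sets the standard: "The independence of this study from any actual or perceived influence, is critical".

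**The concern.** An invitation to a survey should ask for the recipient's experience. This one also asks for help in demonstrating a conclusion, and the request comes from a founder of the company whose product is being rated. Because responders cannot be identified, the reminder goes to all invitees, so people who have not yet answered are sent it before they do.

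Two routes to bias follow. Users well disposed to the product may be more likely to respond, and those who respond may shade their ratings upward. Both would push towards the favourable hypotheses on ease, ability to use, perceived safety and level of concern. The first route could also reach the pregnancy rate, if satisfied users are more often those who conceived. The survey is anonymous and taken once, so a bias from this source cannot be repaired after collection.

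**Working it through.** **1. The plan's own precision figure.** Section 9.2 gives a margin of 4.4 points with 500 surveys and 5 points with 384. The half-width at a proportion of 0.5 is 1.96 × √(0.25/n).

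- n = 500: 1.96 × √(0.25/500) = 0.0438, or 4.4 points.
- n = 384: 1.96 × √(0.25/384) = 0.0500, or 5.0 points.

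Both figures reproduce. They describe sampling error only. A shift caused by the invitation is not in them and does not shrink with a larger sample.

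**2. Who could be affected.** Respondents on Days 0 to 6 have not been sent the second email. Later respondents have been sent it but may not have opened it; section 9.2 cites an open rate of about 20% on general emails. The exposed share of respondents, e, is not in the documents and is varied below.

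**3. Effect through who answers (all inputs assumed).** Let p be the true share with little or no concern, and let r be how many times as likely such users are to answer after the appeal. Among exposed respondents the observed share is s = p·r / (p·r + 1 − p). Over all respondents it is e·s + (1 − e)·p. With p = 0.45:

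| r | s (all exposed, e = 1) | half exposed, e = 0.5 |
|---|---|---|
| 1.1 | 0.495/1.045 = 47.4% | 46.2% |
| 1.25 | 0.5625/1.1125 = 50.6% | 47.8% |
| 1.5 | 0.675/1.225 = 55.1% | 50.1% |

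Reaching 50% needs r = 0.55/0.45 = 1.22 if all are exposed. If half are, s must be 0.55, so r = (0.55 × 0.55)/(0.45 × 0.45) = 1.49. The value p = 0.45 was chosen to lie near the majority threshold of Secondary Hypothesis 5. A true share far from 50% would not change sides.

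**4. Effect through how people answer (all inputs assumed).** If exposed respondents shift by d points, the bias is e × d.

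| Exposed share e | Shift d that gives 4.4 points of bias | Bias if d = 5 points |
|---|---|---|
| 25% | 17.6 | 1.25 |
| 50% | 8.8 | 2.5 |
| 75% | 5.9 | 3.75 |
| 100% | 4.4 | 5.0 |

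The bias matches the plan's stated margin only if the exposed share is high or the shift is large.

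**The case against.** The strongest reply is that the appeal names the importance of home insemination to the industry and says nothing about the kit being easy or safe. A user who found the kit awkward or worrying could agree with it. That stands, and it makes the link to the secondary endpoints indirect.

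Other text pulls the other way. The subject line of the same email asks for help in making the product better, the same sentence asks for help in improving the process, and the first email's subject line invites candour. The survey is anonymous, which lowers the pressure to please. These points offset the appeal in part but do not remove it.

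Nor are the secondary analyses all opinion. Section 9.1 also uses reported use behaviours under Secondary Hypothesis 2, infection rates under 4, and hand washing, syringe disposal and reading of the instructions under 5. Secondary Hypothesis 3 concerns reported timing. These are self-reports, but they are less open to a change of attitude.

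Finally, the emails are samples. That shows the text can be changed, but nothing in the plan commits the sponsor to neutral wording.

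**Conclusion.** The point holds as an avoidable risk of selection and response bias. The second email contains an advocacy appeal, and the plan has no measure against its effect. The direction is plausible and the size is unknown. Under the stated assumptions (p = 0.45, r = 1.25), the little-or-no-concern share crosses one half at full exposure and stays below it at half exposure.

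A reader might infer that the ease and safety endpoints are in fact steered, or that a modest push is enough to reverse Secondary Hypothesis 5. The documents do not support either reading. They give no effect size, the appeal does not mention ease or safety, early respondents and those who never open the email are untouched, and the reversal at 1.25 needs nearly everyone to be exposed. The recommendation is a cheap improvement to the wording.

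**What to change.** In the second email, delete the sentence on IVF research, the short sentence after it that hopes to change this, and the clause quoted above about showing importance. Add a neutral line to all five emails, for example: *We would like to hear from everyone who used the kit, whether your experience was good or bad and whether or not you became pregnant.*

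The sponsor can go on sending the emails, so the privacy arrangement in section 10.1.3 is unchanged. Signing them as the study team is optional and adds limited independence, since section 10.1.12 discloses that the investigator's study is work for hire.

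Optionally, keep submission dates and compare ease and safety ratings before and after Day 7. Early and late responders may differ for other reasons, so a difference would not by itself show an effect of the email.

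The cost is an edit to the templates and their submission to the IRB, plus possibly a slightly lower response. The targets need 384/4000 = 9.6% and 500/4000 = 12.5% of invitees, against the 15% (600 surveys) assumed in section 9.2. That slack holds only if the response comes near 15%. At the low end of the typical range in section 5.5, 5% of 4000 is 200, which is below the minimum whatever the wording.

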9.2 Sample Size Determination

The desired final sample size for this study is 500 completed surveys. This will produce a 95% confidence interval with +/- 4.4% within larger populations. In order to obtain that rate of respondents, the study will invite about 50% people who have ordered a Mosie Kit in the prior 2-8 months to the study start date. It is expected that approximately 4000 people will be invited to participate. By inviting 4000 potential participants, it is expected that with a response rate of 15% approximately 600 will complete the survey. Currently Mosie has about a 20% open rate on their general emails. For this reason, all people who purchased a kit within the last 2-8 months will be invited to participate.

According to the sample size tables, a response rate of 384 is sufficient to provide a 95% confidence interval with a 5% margin of error rate. While the total number of respondents can not be controlled, every effort will be made via the reminder emails to obtain at least 500 participants but no less than 384.

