9.3 Populations for Analyses

The population to be analyzed include any one using the Mosie Kit in the full 2-8 months prior to study commencement. Respondents can be male or female. Overall the data will be analyzed as a whole and stratified by sex (having ovaries and a uterus as indication of being a female), age and type of relationship.

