9.4 Statistical Analyses

9.4.1 General Approach

Statistical analysis will commence with descriptive statistics for each survey question and plotting of the individual data into scatter plots to understand the data distribution. If any information suggests corrective procedures should be employed, the appropriate transformation or non-parametric test will be used.

Categorical values will be reported using descriptive statistics and frequency of occurrence. Key categorical values will also be converted into a percentage of total responses in order to allow an understanding of the prevalence of the response in the sample. For continuous variables, the means with standard deviations, median and range will be reported.

Qualitative data is only expected as a response to two questions, an open ended safety question and an additional comments question. The responses will be evaluated and categorized. Then the frequency of each category will be provided.

For inferential tests such as t-tests and ANOVAs, a p-value of 0.05 and a confidence interval of 95% will be used for statistical significance. The type of hypothesis will determine whether the specific tests will be one-tailed or two-tailed. Hypothesis seeking to understand whether there is or is not a difference will use a two-tailed test while those seeking a greater than or less than relationship will use a one-tailed test. Correlations among some of the variables will also be examined as appropriate.

Statistical analysis process for each hypothesis has already been described in section 9.1. No baseline analysis is used for cross-sectional studies. No interim analyses are planned for cross-sectional one survey studies.

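### No safeguard is described against one conception attempt being recorded more than once; the loss of precision would be small, but outcome-related repeats could shift the pregnancy rate either way

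*Combined protocol and SAP*

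**What the plan says.** - **Link and reminders.** Section 10.1.3: "Participants will receive an invitation email with a generic link to the study website". No identifier is collected. Section 5.5 schedules five emails, with weekly ones if the study is extended, and Section 10.1.2 allows collection for up to 90 days. The third email in Appendix C explains why reminders keep coming: "It is anonymous so we have no idea if you already have".
- **Who may answer.** Section 9.3: "Respondents can be male or female". Many items in Appendix A are worded for the respondent or the partner, and the infection item may be answered on behalf of the person trying to conceive.
- **Checks.** The automatic screen covers only age and kit use (Section 5.4). Having an email on file is not verified (Section 5.1). Data checks are limited to field type and completeness, and no outside records are linked (Section 10.1.9.1).
- **Intention.** The synopsis says each participant is asked for one survey. No means of enforcing this is described, and it does not cover two partners completing one each.
- **Endpoint and precision.** Whether use of the kit led to a pregnancy is a single yes/no item per submission (Appendix A). Section 9.1 compares the total rate with 10–20% for IUI. Section 9.2: "The desired final sample size for this study is 500 completed surveys"; "This will produce a 95% confidence interval with +/- 4.4% within larger populations". Sections 9.1 to 9.4 make no allowance for repeated or paired records.

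**The concern.** The protocol does not define the counting unit of the primary endpoint beyond asking how many people become pregnant. On any sensible reading one pregnancy should count once. The database holds submissions, and nothing visible ties a submission to a single user or couple. A responder who misreads a reminder, or a partner who opens the same link, adds a second truthful record of the same outcome.

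Two things follow. The confidence interval treats both records as independent, so it is too narrow. And if the tendency to answer twice depends on whether a pregnancy occurred, the rate itself is biased, which a larger sample would not cure. Because no follow-up is possible, the information needed to recognise duplicates must be collected in the survey or it is lost.

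**Working it through.** **1. The plan's own figure.** Inputs from Section 9.2: n = 500, 95% confidence. The proportion is not stated; p = 0.5 reproduces both figures.

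- Margin = 1.96 × √(0.5 × 0.5 / 500) = 4.38 points (stated 4.4).
- n for ±5 points = 0.25 × (1.96 / 0.05)² = 384 (stated 384).

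Both agree. This is the formula for independent responses, with no finite-population correction (with N = 4000 it would give 4.10).

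**2. Precision with duplicates.** Assumption: a fraction d of couples or users supply two records with the same outcome. The 500 records then come from 500/(1+d) units, the sum of squared unit sizes is 500(1+3d)/(1+d), and

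effective n = 500² / [500(1+3d)/(1+d)] = 500(1+d)/(1+3d).

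| d (assumed) | Effective n | Margin at p = 0.5 | Margin at p = 0.2 |
|---|---|---|---|
| 0 | 500 | 4.4% | 3.5% |
| 5% | 525/1.15 = 457 | 4.6% | 3.7% |
| 10% | 550/1.30 = 423 | 4.8% | 3.8% |
| 20% | 600/1.60 = 375 | 5.1% | 4.0% |

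If the fraction is defined per submission, the design effect is 1 + 2d, and about 15% of submissions must be repeats before 500 surveys perform like 384 independent ones.

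**3. Bias.** Let r₁ and r₀ be the chances of a second record with and without a pregnancy (assumed). Expected observed rate = p(1+r₁) / [p(1+r₁) + (1−p)(1+r₀)]. With a true p of 0.20, the top of the Section 9.1 reference range:

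- r₁ = 10%, r₀ = 0: 0.22 / (0.22 + 0.80) = 21.6%
- r₁ = 0, r₀ = 10%: 0.20 / (0.20 + 0.88) = 18.5%
- r₁ = r₀ = 10%: 0.22 / (0.22 + 0.88) = 20.0%

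**4. Effect on a test.** Section 9.1 names no formal test for this comparison. As an illustration, a one-sided 0.05 test of 500 submissions against 20% was simulated with the true rate at 20%. It rejected in about 5% of runs with no duplicates, 7% with 10% outcome-neutral repetition, and 25% when 10% of conceiving users alone repeated. The shift of about 1.6 points explains most of the last figure: the standard error is √(0.2 × 0.8 / 500) = 1.8 points.

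**The case against.** Several stronger readings are tempting, and the documents do not support them.

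- *That the stated precision is wrong.* It is not. The 4.4% is the worst case at p = 0.5. At a 20% rate every margin in the table stays inside it. Section 9.2 also expects about 600 completions; with 10% of couples doubled, effective n would be 600 × 1.1 / 1.3 = 508, and the margin still about 4.3% at p = 0.5.
- *That repeat submission is rewarded.* Every sample email offers 15% off, but the reward is one static code that is also used in other marketing (Section 2.3.2, Appendix A). A second submission earns nothing new. Confusion over reminders, or a partner answering, is the likelier route.
- *That the link is known to accept repeat submissions.* The text says generic. Reuse is inferred from the absence of any described token or limit. The form screenshots and FAQ text are not visible, so a form setting or a respond-once instruction cannot be ruled out. A limit per person would still not stop a second partner.
- *That the pregnancy rate will be inflated.* No duplication rate is given and its relation to outcome is unknown; the bias may be upward, downward or nil.

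It can also be said that invitations go to purchasers, so a partner normally enters only through a shared or forwarded link; that the proxy wording fits one respondent reporting for both; that single users have no partner to duplicate them; and that the third email, read in full, thanks earlier responders, explains the reminders and offers an opt-out. All of this lowers the likely frequency. It does not supply a safeguard. Anonymity was a reasoned choice in Section 10.1.3, and the remedy should respect it.

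**Conclusion.** The point holds as a gap in data collection, not as an error in the sample-size arithmetic. The documents describe a route by which one conception attempt can be recorded twice and, in the text that is visible, nothing that prevents or detects it. The precision cost is minor: 0.2 to 0.4 points at p = 0.5 if 5–10% of couples are doubled. The possible bias matters more, about +1.6 or −1.5 points on a true 20% rate if 10% of one outcome group alone repeats, and none if repetition is unrelated to outcome. These sizes rest on assumed duplication rates and on both records reporting the same outcome. The improvement is worth making because it is cheap and cannot be made after collection.

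**What to change.** Add one question to the automatic eligibility screen in Section 5.4: *Have you or your partner already submitted this survey?* A Yes ends the survey, as the age and kit-use questions already do. State in every email that one response per couple or user is wanted and that anyone who has already answered should not answer again.

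Optionally, pre-specify a sensitivity analysis of the primary rate that drops later records identical to an earlier one on the detailed cycle-by-cycle answers and outcome. Do not require a demographic match, since partners will usually differ on gender and often on age or race. Report with it that unrelated users may match by chance, so some genuine records may be dropped.

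The cost is one question, one line per email and one extra analysis run, with IRB review of the changed materials. Appendices A and C already foresee changes of wording. Anonymity is kept. The limitation is that the screen relies on honest answers, so it reduces duplicates and does not remove them.
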